5. STUDY DESIGN

STRIDER NZAus is a bi-national multicentre double blind randomised placebo controlled trial with intention-to-treat analysis.

5.1 Participating Centres:

Subjects will be recruited from Maternal Fetal Medicine centres across New Zealand and Australia. Each centre will nominate local investigators to oversee local recruitment.

The STRIDER NZAus trial will be coordinated by staff at The University of Auckland. Staff at the Auckland coordinating centre will include the STRIDER NZAus Principal Investigator and Lead Investigators, STRIDER NZAus Clinical Trial Manager, research midwives, research fellow (responsible for myometrial and placental studies) and any other staff required to support clinical trial activities or analysis.

5.2 STRIDER IPD Collaboration

Study design and outcome measures are aligned with other planned STRIDER trials in Ireland/United Kingdom, Canada and the Netherlands. Each trial will be funded and managed individually but results will be used in an international collaboration of IPD analysis (STRIDER IPD Collaboration). This prospectively planned IPD will have sufficient power to assess the effect of sildenafil on rates of survival without major morbidity in pregnancies complicated by severe early onset IUGR.

6. STUDY POPULATION – Inclusion & Exclusion Criteria

Women with pregnancies affected by severe early onset IUGR will be identified from MFM clinics in each recruiting centre.

6.1 Inclusion Criteria:

1. Singleton pregnancy.
- 2a. $\geq 22^0$ weeks and $\leq 27^6$ weeks: AC measure $\leq 3^{\text{rd}}$ percentile for gestational age; OR
- 2b. $\geq 28^0$ weeks and $\leq 29^6$ weeks: ultrasound estimate of fetal weight (EFW) $< 700\text{g}$.

These criteria have been set in line with the STRIDER IPD Collaboration.

AC percentile must be calculated using ASUM Campbell Westerway chart [12]. EFW must be calculated using the Hadlock C formula [13].

6.2 Exclusion Criteria:

1. Known major fetal anomaly/syndrome/congenital infection that is deemed to be the likely cause for IUGR.
2. Known fetal aneuploidy (if untested for aneuploidy are eligible for the trial).
3. Already made plan for termination of pregnancy.
4. Maternal disease (e.g. preeclampsia) where it is expected that delivery is necessary within next 48 hours.
5. Any contraindication to sildenafil therapy.

These criteria have been set in line with the STRIDER IPD Collaboration.

6.3 Withdrawal of subjects

All study participants are free to discontinue the study drug and/or withdraw their consent at any point during treatment without prejudice. If a subject indicates that they wish to withdraw their consent for further participation data collected to the point of withdrawal will be retained and used as part of the intent to treat analysis. The Investigator is encouraged to ask a subject who is withdrawing which level of continued participation they agree to. Subjects who elect to discontinue the study drug early (subject initiated discontinuation prior to 32 weeks or delivery), may continue their participation in one of the following ways:

1. Early discontinuation of study drug but continue with all other trial involvement.
2. Early discontinuation of study drug, continued collection of data from clinical records and follow up contact to 6-12 weeks after delivery.
3. Early discontinuation of study drug, continued collection of data from clinical records only. No follow up contact.
4. Complete withdrawal of consent, i.e. early discontinuation of study drug, no further collection of data from clinical records and no follow up contact. If a subject specifically requests complete withdrawal of consent publically available information only such as from the Birth Register may still be accessed to collect survival status.

The level of continued follow up data collection a subject will permit must be recorded in the CRF. Wherever possible the reason for study treatment discontinuation or withdrawal of consent should be recorded in the CRF. All subjects will receive ongoing medical care according to clinical need.

7. STUDY NUMBERS & POWER CALCULATION

7.1 STRIDER NZAus study

Assuming 50% (placebo-treated) vs 80% (sildenafil-treated) increased post-randomisation AC growth velocity, with an α of 0.05, two sided, we will have 90% power to detect this difference if we randomise 58 women per group.

Allowing for a 5% drop-out rate, the **total sample size required is 122 women.**

7.2 STRIDER IPD Collaboration

To be confirmed by STRIDER IPD Collaboration. Example: Assuming a 21% (placebo-treated) vs 35% rate of survival free of major handicap at the time of hospital discharge or EDD, whichever is later, (sildenafil-treated), with an α of 0.05, two sided, we will have 90% power to detect this difference if a total of 504 women are randomised at a ratio of 1:1 (229 in each treatment arm and 10% drop-out rate). STRIDER NZAus will contribute 122 cases to this IPD analysis.

7.3 Feasibility of recruitment

In a retrospective audit of deliveries 20⁺⁰ to 29⁺⁶ weeks at National Women's Hospital, Auckland 2006-2010 (inclusive), a total of 271 pregnancies were identified. However, only 53 cases met the study inclusion criteria and had the criteria identified before delivery. Allowing for some women who would meet inclusion criteria but deliver after 30 weeks, it is likely that 10-15 eligible cases will be seen at National Women's Health per year.

8. SUBJECT SELECTION & RECRUITMENT

Due to the very high risk nature of these pregnancies, women who are eligible for the STRIDER NZAus study are expected to be under the care of the Maternal Fetal Medicine high risk teams in each recruiting centre. Once women have been identified as eligible by meeting the inclusion criteria (and have no exclusion criteria) they will be provided with information regarding the trial. This will be done verbally and with a written information sheet and consent form provided by the study investigators.

All women will be given time for full consideration and consultation as required. Contact telephone numbers will be provided. Study investigators or the research midwife will then meet with the potential recruit again and if women wish to join the study the consent process, randomisation and first visit will be completed. Signed, written consent must be obtained by the subject in the presence of a Study Investigator.

For women who decline to take part in this drug trial antenatal care will continue to the same standard as for all women with this condition. Sildenafil will not be available as part of this standard of care.

Only after declining participation these women will be invited to contribute to the study by collection of data only. This should only be offered once women have had time to fully consider participation in the randomised trial and have formally declined. Signed consent for the collection of data only must be provided by the subject and Study Investigator (on the Declined Randomisation – Observational Group information sheet and consent form). Refer section 14 of the protocol for details of data collection for this group.

9. RANDOMISATION

This will be performed using a web-based randomisation service operating at British Columbia Women's Hospital (Vancouver, Canada). Randomisation will be stratified for;

1. Gestational age at recruitment (< or ≥ 24 weeks)
2. Present or absent/reversed end-diastolic flow in umbilical artery Doppler waveform.

Women will be randomised on a 1:1 ratio to sildenafil:placebo. The randomisation process will assign each subject with a unique study ID number. This study ID number will be required when allocating study drug containers and for recording data on the CRF. The randomisation service provides 24 hour access, 7 days per week.

If a woman is found not to be eligible for the trial when her details are entered into the randomisation program the program will return a screen failure notification. Potential subjects who have screen failed can be re-screened for eligibility and included in the trial at a later date if appropriate.

10. TREATMENT GROUPS & STUDY DRUG

10.1 Treatment groups

Women will be randomised to one of two groups:

1. *Sildenafil*
Oral sildenafil citrate 25mg three times daily (tds).

OR

2. *Placebo*
Matching placebo tablets containing no active ingredient three times daily (tds).

Participants, medical professionals caring for women and study investigators will remain blinded to treatment allocation until the study is completed and database lock has occurred.

These dosing regimens have been set in line with the STRIDER IPD Collaboration.

10.2 Drug Supply and Storage

Each study drug container will contain 30 tablets, equivalent to a 10 day supply. Both sildenafil and identical placebo tablets (containing no sildenafil citrate) will be sourced from a single supplier (Actavis). It will be packaged centrally (Anquai, School of Pharmacy, University of Auckland) and distributed to each study site according to requirement.

The Investigator at each site is responsible for study drug inventory and accountability throughout the trial. The study drug must be stored in a limited access area or locked cabinet. Storage should be in a temperature controlled area below 25°C.

10.3 Drug Issue and assessment of Compliance

At the time of randomisation the study drug allocation program (web based) will assign the first study drug container. Study drug will be re-issued as required thereafter by the study investigators and/or delegated study staff such as a research midwife. Subjects will be asked to return used and unused medication containers for regular 'pill count' to assess compliance. Women will also be asked to record their study drug usage in a subject medication diary (SMD).

10.4 Emergency Unblinding

In the event that there is an immediate need for the treating doctor to know a subject's treatment allocation in order to ensure patient safety it will be possible to break the randomisation code. The facility to perform emergency unblinding will be available 24 hours per day. It is recommended that the Investigator contact the Auckland Principal Investigator to discuss the particular situation before breaking the subject's randomisation code, if possible.

11. TREATMENT DURATION/INDICATIONS TO STOP TREATMENT

11.1 Treatment duration

Study drug treatment will commence as soon as possible following randomisation and continue tds until delivery or 32⁰ weeks gestation (or intrauterine demise). Due to the nature of this condition and the inclusion criteria set it is unlikely that pregnancies will proceed beyond 32⁰ weeks i.e. fetal compromise will determine that earlier delivery is necessary. In the event that a woman remains pregnant at 32⁰ weeks treatment will be stopped as neonatal outcomes beyond this gestation are generally very good and so it will no longer be appropriate to continue to use the study drug.

[figure not shown]
11.2 Additional indications to stop treatment

1. Severe maternal hypotension causing maternal and/or fetal compromise in the absence of other anti-hypertensive drug use (i.e. stop other antihypertensives first).
2. If the Investigator believes that it is in the best interests of the subject for safety or tolerability reasons (e.g. due an Adverse or Serious adverse event).
3. Subject request to discontinue study drug.

12. STUDY PROCEDURES & SUBJECT FLOW CHART

The study procedures are summarised in the flow chart below and in the schedule of assessments (Appendix 1).

Individual Subject Trial Flow Chart

12.1 Baseline data collection

Medical history and demographics: data will be collected on current and past medical history and demographics including date of birth, ethnicity, height and weight, past obstetric history, past medical history, medication use, details of aneuploidy screening and invasive tests and fetal infection screen.

Previous Ultrasound Scan (USS) data: the abdominal circumference (AC) measurement will be collected from the two most recent scans available (not including the randomisation scan). If multiple AC measurements are available one of the documented AC measurements should be from a scan > 12 days and as close to 14 days prior to randomisation.

Maternal assessments:

- Blood test results performed ≤ 24 hours prior to randomisation will be collected including: Full Blood Count (platelets), renal (creatinine, urea, urate) and liver function (AST, ALT, albumin).
- Urinalysis results performed ≤ 24 hours prior to randomisation will be collected.
- The highest blood pressure recording from the day of randomisation, prior to study drug treatment, will be collected.

Randomisation USS:

An USS must be performed ≤ 24 hours prior to randomisation and should include the following:

- Fetal growth measurements: abdominal circumference (AC), biparietal diameter (BPD), head circumference (HC) and femur length (FL).
- Amniotic fluid measurement: single deepest vertical pocket.
- Doppler waveforms: umbilical artery (PI and presence/absence or reversed end diastolic flow) umbilical vein (pulsatile or non-pulsatile), ductus venosus (PI, presence of positive a wave), middle cerebral artery (MCA) (PI, PSV) and maternal uterine artery (PI, presence of notch).

Informed consent should be obtained before any study procedures which are not otherwise clinically indicated are performed or repeated for the purpose of meeting trial eligibility.

12.2 Study Drug Treatment Phase

Standard clinical management should be carried out at the discretion of the Investigator. It is anticipated that in many cases clinical assessments and scans will be required more frequently than the study protocol requires.

The study protocol time points are 48 hours, 5 days, 10 days, 14 days and weekly thereafter post-randomisation. With the exception of the first post-treatment study assessment which must be conducted as close as possible to 48 hours post-randomisation, routine clinical assessment and scan data can be used and the

assessment results closest to the protocol time points should be collected (recommended to be within +/- 2 days).

Maternal Assessment

The following assessments will be completed at 48 hours (BP only), days 5, 10, 14 and then weekly following randomisation:

- Blood pressure measurement.
- Dipstick urinalysis +/- Protein/Creatinine ratio or 24 hour urine collection.
- Blood tests including: Full blood count (platelets), renal (creatinine, urea, urate) and liver (AST, ALT, albumin) function.
- Concomitant medication review.
- Review of study drug compliance and SMD.
- Adverse Event/Serious Adverse Event assessment.
- Review of antenatal management.

Fetal Assessment

Ultrasound Scan

Following randomisation an USS should be performed at 48 hours, days 5, 10, 14 and then continued on a weekly basis and should include the following:

- Fetal growth measurements: AC, BPD, HC and FL.
- Amniotic fluid measurement: single deepest vertical pocket.
- Doppler waveforms: UA (PI and presence/absence or reversed end diastolic flow) UV (pulsatile or non-pulsatile), DV (PI, presence of positive a wave), MCA (PI, PSV) and maternal uterine artery (PI, presence of notch).

USS scans are performed in routine clinical practice in assessment of severe IUGR and will follow standard protocols (as described in the Ultrasound Imaging Manual).

Computerised CTG

Once the fetus has reached viability i.e. >24 weeks and EFW >500g, confirmed by medical team caring for each individual (with consideration for corticosteroids), a weekly computerised CTG will be performed to record short term variability, if available at the study site.

The above maternal and fetal assessments should continue until study drug treatment is discontinued or delivery occurs, whichever comes first. If study drug treatment is discontinued prior to delivery an additional post-treatment assessment should be carried out greater than 48 hours (but within 10 days) after the last dose of study drug.

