16. OUTCOME MEASURES

16.1 Primary Outcome

The primary outcome is increase in fetal growth velocity.

Fetal growth velocity will be determined by AC growth velocity. Mean daily increase in AC (calculated as a proportion to that expected if AC were on 50th centile for gestational age) pre and post treatment will be compared.

Pre-treatment growth velocity epoch will be calculated from: most recent AC measurement >12 days and recruitment AC measure. Where there is no previous scan with recorded AC, the AC will have been assumed to lie on 50th centile at 8 weeks gestation.

Post-treatment growth velocity epoch will be calculated from: the recruitment AC measure and a 14 day AC measure, where delivery has occurred before 14 days the longest interval shall be used (10, 5 and finally 2 days).

The proportions with increased AC growth velocity in the sildenafil group and placebo group will be compared.

This primary outcome has been selected in line with the STRIDER IPD Collaboration.

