17. STATISTICAL ANALYSES

Data will be analysed on an intention-to-treat basis.

Demographic and other baseline data will be summarised by study treatment groups. For continuous outcomes, t-test, linear regression and mixed model for repeated measures method will be used where appropriate. For categorical outcomes, Fisher's exact test, logistic regression and generalised linear mixed effects model will be used where appropriate. Two sided-p-values less than 0.05 will be used to determine statistical significance and all confidence intervals will be reported at a two sided 95% level.

Details of statistical analysis method are described in the Statistical Analysis Plan.

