Appendix 1 - Schedule of assessments and procedures for randomised subjects.

Study assessment/procedure	Screening & Randomisation CRF 1,2,3	Double-Blind Treatment Period				48 hours post-treatment** (if not delivered) CRF 5	Delivery CRF 7,8	Postnatal (discharge /neonatal EDD) CRF 8,9	Follow Up 6-12 weeks postpartum CRF11
		48 hours post-randomisation CRF 4	Day 5* CRF 5	Day 10* CRF 5	Day 14* & weekly* to delivery CRF 5				
Review of Eligibility	X								
Informed Consent	X								
Demographics	X								
Medical/Obstetric History	X								
Current Pregnancy Characteristics	X								
USS ¹	X	X	X	X	X	X			
Blood Pressure	X	X	X	X	X	X			
Urinalysis ²	X		X	X	X	X			
FBC, Renal function, LFTs ³	X		X	X	X	X			
Concomitant Medication review	X		X	X	X	X			
Randomisation	X								
Issue of Study Drug ⁴	X		← X →						
Review of Study Drug compliance & SMD			X	X	X	x	x		
Adverse Event/Serious Adverse Event Assessment ⁵		X	X	X	X	X	X		
Review of Antenatal Management			X	X	X	X	X		
Computerised CTG short term variability ⁶			x	x	x	x			
Placental & Myometrial biopsy (Auckland centre only) ⁷							x		
Labour and Delivery details							X		
Maternal & Neonatal outcomes to hospital discharge/EDD							X	X	
Postpartum Questionnaire								X	

1. Screening ultrasound must be performed <24 hours prior to randomisation. AC measurement will also be collected from previous scans, if available. Detail on scanning parameters is located in the Ultrasound Imaging Manual.
2. Screening Urinalysis to be performed <24 hours prior to randomisation: dipstick protein analysis (required); Protein/Creatinine ratio and/or 24 hour urinary protein (if performed).
3. Screening Blood tests to be performed <24 hours prior to randomisation: Platelets, Creatinine, Urea, Urate, AST, ALT, Albumin.
4. Study drug to commence as soon as possible after randomisation and to continue until physician decision for delivery, Intrauterine death, participant request for withdrawal, physician decision to stop study drug or 32⁰ weeks gestation. Study drug should be re-issued as required.
5. AE/SAEs to be collected from the time of randomisation through to maternal hospital discharge after delivery; fetal/neonatal death occurring prior to discharge or EDD; neonatal hospital discharge or EDD, whichever is later.
6. Computerised CTG to be performed weekly once the fetus has been determined as viable by the participant's medical team, if available.

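### Section 12.2 ends required scans when study drug stops, so a day-14 AC is not assured for undelivered women who stop early, and section 16.1 has no rule for them

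*Protocol*

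**What the plan says.** Section 12.2 sets AC and Doppler scans at 48 hours, days 5, 10 and 14, and weekly after that. It closes the schedule with: "The above maternal and fetal assessments should continue until study drug treatment is discontinued or delivery occurs, whichever comes first". If drug stops before delivery, "an additional post-treatment assessment should be carried out greater than 48 hours (but within 10 days) after the last dose of study drug". Appendix 1 includes an ultrasound scan in that visit.

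Section 16.1 calculates the post-treatment growth epoch from "the recruitment AC measure and a 14 day AC measure". Its fallback reads: "where delivery has occurred before 14 days the longest interval shall be used (10, 5 and finally 2 days").

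Three other places bear on whether scanning continues after drug stop:

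- Section 6.3, first level of continued participation: "Early discontinuation of study drug but continue with all other trial involvement". The second level is "Early discontinuation of study drug, continued collection of data from clinical records and follow up contact to 6-12 weeks after delivery".
- Appendix 1 heads the relevant scan column "Day 14* & weekly* to delivery CRF 5".
- Section 17: "Data will be analysed on an intention-to-treat basis". Section 5 makes the same commitment.

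**The concern.** An intention-to-treat comparison needs the outcome measured in every randomised woman at the same time, on or off drug. Section 12.2 ties required measurement to drug exposure. A site following that sentence may stop study scans that a site following Appendix 1 would perform.

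The reasons for stopping in section 11.2 include maternal hypotension, safety and tolerability, and the woman's own request. The first two could be commoner on a vasodilator, and any of them could track prognosis. AC values missing for these reasons may be informative and may differ between arms. The sample size in section 7.1 allows 5% for drop-out, and early stoppers without an AC would draw on that same allowance.

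**Working it through.** **1. The plan's own sample size.** Inputs from section 7.1: 50% versus 80%, two-sided alpha 0.05, power 90%.

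- Uncorrected: n = [1.960·√(2·0.65·0.35) + 1.282·√(0.5·0.5 + 0.8·0.2)]² / 0.30² = 51.01, so 52 per group.
- With continuity correction: n' = (51.01/4)·[1 + √(1 + 4/(51.01·0.30))]² = 57.5, so 58 per group, as stated.
- Drop-out: 116·1.05 = 121.8 and 116/0.95 = 122.1. The stated total of 122, or 61 per arm, is consistent within rounding.

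**2. Can the off-drug scan replace the day-14 scan?** For a last dose on day d, that assessment falls after day d+2 and no later than day d+10. Section 12.2 recommends ±2 days around a time point, so the day-14 window is days 12 to 16.

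| Last dose (day) | Off-drug scan falls between | Within days 12–16? | On day 14 itself? |
|---|---|---|---|
| 0–1 | day 2 and day 11 | no | no |
| 2–3 | day 4 and day 13 | possible | no |
| 4–11 | day 6 and day 21 | possible | possible |
| 12–13 | day 14 and day 23 | possible | no (more than 48 hours needed) |

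For no stopping day before day 14 does the requirement guarantee a scan at day 14. For stops on days 0–1 the required scan cannot reach even the ±2-day window.

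**3. Does section 16.1 cover her?** Its substitution of days 10, 5 and 2 is conditional on delivery before day 14. A woman who stopped drug and is still pregnant does not meet that condition, even if she has an AC from day 2, 5 or 10. Nor does the rule give a place to an off-drug scan on, say, day 8.

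**4. Power if every early stopper lost her AC.** The protocol gives no early-stop rate, so 5 to 20% is an assumption. Exact Fisher power, 50% versus 80%, two-sided 0.05, equal loss in both arms and no other loss:

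| Lost | Left per arm, 61·(1 − loss) | Power |
|---|---|---|
| 0% | 61 | 91.9% |
| 5% | 57.95, about 58 | 90.6% |
| 10% | 54.9, about 55 | 89.1% |
| 15% | 51.85, about 52 | 86.9% |
| 20% | 48.8, about 49 | 84.2% |

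**5. Illustration of bias.** Take a true rate of 50% in both arms, with loss in one arm only. If a share m is lost and a proportion r of those women would have responded, the observed rate in that arm is (0.50 − m·r)/(1 − m).

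- m = 10%: r = 30% gives (0.50 − 0.03)/0.90 = 52.2%; r = 0 gives 0.50/0.90 = 55.6%.
- m = 20%: r = 30% gives (0.50 − 0.06)/0.80 = 55.0%; r = 0 gives 0.50/0.80 = 62.5%.

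The values of m and r are assumptions chosen to show the range.

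**The case against.** A reader might infer that the primary outcome cannot be analysed by intention to treat, or that the trial becomes an on-treatment comparison. The documents do not support that. Nothing excludes discontinuers from the analysis. Section 6.3 keeps data up to withdrawal for the intention-to-treat analysis, and its first three levels all continue data collection after drug stop. Section 12.2 allows routine scans to be used from day 5 and expects many women to be scanned more often than the protocol requires. Section 12.3 expects intense fetal surveillance in all these women. One off-drug scan is required and may fall near day 14, and an AC from day 2, 5 or 10 may also exist. These points stand: not required does not mean lost.

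They do not close the gap. The permission to use routine scans concerns time points in the treatment phase, which section 12.2 ends at drug stop. Section 12.3 does not promise an AC. The levels in section 6.3 are written for discontinuation by the woman's choice, and stops by the investigator under section 11.2 have no matching provision.

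The Appendix 1 column sits under the treatment-period banner, so it can be read as applying only on drug. Its own wording nevertheless runs to delivery, and the two readings need settling.

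Finally, the analysis of a woman without a day-14 AC may be set out in the statistical analysis plan, which is not available here. That could answer the missing fallback, but an analysis plan cannot create scans that the protocol does not require.

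**Conclusion.** The point holds as a conflict over data collection. Section 12.2 ends required scans at drug stop, against section 6.3 (first level), Appendix 1 and the intention-to-treat commitment, and section 16.1 gives no rule for the undelivered woman who stopped early. The intention-to-treat analysis is put at risk of informative missing data; it is not made impossible.

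The size cannot be fixed because the early-stop rate is not stated. The power figures assume that every early stopper loses her AC, so at each assumed rate they are an upper bound on the power cost of this gap alone. A 5% loss stays within the planned allowance and leaves 90.6%; a 20% loss leaves 84.2%, about 6 points below the 90% target. Bias is the more serious issue, because a larger sample would not remove it. It arises only if missingness is related both to arm and to the outcome, which section 11.2 makes plausible but does not show.

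**What to change.** Reconcile the closing sentence of section 12.2 with section 6.3 and Appendix 1. Outcome AC and Doppler scans at 48 hours, days 5, 10 and 14, and weekly to delivery should be collected whether or not study drug is being taken. Routine scans would be allowed as section 12.2 already provides, and collection would remain subject to the level of participation the woman chooses. State that this applies to stops by the investigator as well as by the woman. Keep the post-treatment visit as an addition.

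In section 16.1, extend the shorter-interval rule to any woman without a day-14 AC, whatever the reason.

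The cost is a short amendment and some extra scan data collection, mostly of scans that section 12.2 describes as routine practice. The sample size stays at 122, and no treatment or stopping rule changes.
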